5.2.1 Adverse Events

According to the ICH guideline for Good Clinical Practice, an adverse event is any untoward medical occurrence in a clinical investigation subject administered a pharmaceutical product, regardless of causal attribution. An adverse event can therefore be any of the following:

- Any unfavorable and unintended sign (including an abnormal laboratory finding), symptom, or disease temporally associated with the use of a medicinal product, whether or not considered related to the medicinal product
- Any new disease or exacerbation of an existing disease (a worsening in the character, frequency, or severity of a known condition) (see Sections [5.3.5.8](#) and [5.3.5.9](#) for more information)
- Recurrence of an intermittent medical condition (e.g., headache) not present at baseline

- Any deterioration in a laboratory value or other clinical test (e.g., ECG, X-ray) that is associated with symptoms or leads to a change in study treatment or concomitant treatment or discontinuation from study drug
- Adverse events that are related to a protocol-mandated intervention, including those that occur prior to assignment of study treatment (e.g., screening invasive procedures such as biopsies)

5.2.2 Serious Adverse Events (Immediately Reportable to the Sponsor)

A serious adverse event is any adverse event that meets any of the following criteria:

- Is fatal (i.e., the adverse event actually causes or leads to death)
- Is life threatening (i.e., the adverse event, in the view of the investigator, places the patient at immediate risk of death)

This does not include any adverse event that, had it occurred in a more severe form or was allowed to continue, might have caused death.

- Requires or prolongs inpatient hospitalization (see Section [5.3.5.10](#))
- Results in persistent or significant disability/incapacity (i.e., the adverse event results in substantial disruption of the patient's ability to conduct normal life functions)
- Is a congenital anomaly/birth defect in a neonate/infant born to a mother exposed to study drug
- Is a significant medical event in the investigator's judgment (e.g., may jeopardize the patient or may require medical/surgical intervention to prevent one of the outcomes listed above)

The terms "severe" and "serious" are not synonymous. Severity refers to the intensity of an adverse event (e.g., rated as mild, moderate, or severe; see Section [5.3.3](#)); the event itself may be of relatively minor medical significance (such as severe headache without any further findings).

Severity and seriousness need to be independently assessed for each adverse event recorded on the eCRF.

Serious adverse events are required to be reported by the investigator to the Sponsor immediately (i.e., no more than 24 hours after learning of the event; see Section [5.4.2](#) for reporting instructions).

5.2.3 Adverse Events of Special Interest (Immediately Reportable to the Sponsor)

Adverse events of special interest are required to be reported by the investigator to the Sponsor immediately (i.e., no more than 24 hours after learning of the event; see Section 5.4.2 for reporting instructions). Adverse events of special interest for this study are as follows:

- Any serious infection, any infections requiring IV antimicrobials, and any opportunistic infections
- Bleeding events of moderate or greater severity
- Any malignancies
- Adverse events of special interest for general drug development
- Laboratory result of AST or ALT $> 5 \times$ ULN
- Cases of potential drug-induced liver injury that include an ALT or AST $> 3 \times$ ULN in combination with a total bilirubin $> 2 \times$ ULN (of which at least 35% is direct bilirubin) or clinical jaundice, as defined by Hy's Law (see Section 5.3.5.6)
- Suspected transmission of an infectious agent by the study drug, as defined below
 - Any organism, virus, or infectious particle (e.g., prion protein transmitting transmissible spongiform encephalopathy), pathogenic or non-pathogenic, is considered an infectious agent. A transmission of an infectious agent may be suspected from clinical symptoms or laboratory findings that indicate an infection in a patient exposed to a medicinal product. This term applies only when a contamination of the study drug is suspected.

5.3 METHODS AND TIMING FOR CAPTURING AND ASSESSING SAFETY PARAMETERS

The investigator is responsible for ensuring that all adverse events (see Section 5.2.1 for definition) are recorded on the Adverse Event eCRF and reported to the Sponsor in accordance with instructions provided in this section and in Sections 5.4–5.6.

For each adverse event recorded on the Adverse Event eCRF, the investigator will make an assessment of seriousness (see Section 5.2.2 for seriousness criteria), severity (see Section 5.3.3), and causality (see Section 5.3.4).

5.3.1 Adverse Event Reporting Period

Investigators will seek information on adverse events at each patient contact. All adverse events, whether reported by the patient or noted by study personnel, will be recorded in the patient's medical record and on the Adverse Event eCRF.

After informed consent has been obtained but prior to initiation of study drug, only serious adverse events caused by a protocol-mandated intervention (e.g., invasive procedures such as biopsies, discontinuation of medications) should be reported (see Section 5.4.2 for instructions for reporting serious adverse events).

After initiation of study drug, all adverse events will be reported until 4 weeks after the final dose of study drug.

Instructions for reporting adverse events that occur after the adverse event reporting period are provided in Section 5.6.

5.3.2 Eliciting Adverse Event Information

A consistent methodology of non-directive questioning should be adopted for eliciting adverse event information at all patient evaluation timepoints. Examples of non-directive questions include the following:

"How have you felt since your last clinic visit?"

"Have you had any new or changed health problems since you were last here?"

5.3.3 Assessment of Severity of Adverse Events

Table 3 provides guidance for assessing adverse event severity.

Table 3 Adverse Event Severity Grading Scale

Severity	Description
Mild	Discomfort noticed, but no disruption of normal daily activity
Moderate	Discomfort sufficient to reduce or affect normal daily activity
Severe	Incapacitating with inability to work or to perform normal daily activity

Note: Regardless of severity, some events may also meet seriousness criteria. Refer to definition of a serious adverse event (see Section 5.2.2).

5.3.4 Assessment of Causality of Adverse Events

Investigators should use their knowledge of the patient, the circumstances surrounding the event, and an evaluation of any potential alternative causes to determine whether an adverse event is considered to be related to the study drug, indicating "yes" or "no" accordingly. The following guidance should be taken into consideration (see also Table 4):

- Temporal relationship of event onset to the initiation of study drug
- Course of the event, with special consideration of the effects of dose reduction, discontinuation of study drug, or reintroduction of study drug (as applicable)
- Known association of the event with the study drug or with similar treatments
- Known association of the event with the disease under study

- Presence of risk factors in the patient or use of concomitant medications known to increase the occurrence of the event
- Presence of non-treatment-related factors that are known to be associated with the occurrence of the event

Table 4 Causal Attribution Guidance

Is the adverse event suspected to be caused by the study drug on the basis of facts, evidence, science-based rationales, and clinical judgment?	
YES	There is a plausible temporal relationship between the onset of the adverse event and administration of the study drug, and the adverse event cannot be readily explained by the patient's clinical state, intercurrent illness, or concomitant therapies; and/or the adverse event follows a known pattern of response to the study drug; and/or the adverse event abates or resolves upon discontinuation of the study drug or dose reduction and, if applicable, reappears upon re-challenge.
NO	An adverse event will be considered related, unless it fulfills the criteria specified below. Evidence exists that the adverse event has an etiology other than the study drug (e.g., preexisting medical condition, underlying disease, intercurrent illness, or concomitant medication); and/or the adverse event has no plausible temporal relationship to administration of the study drug (e.g., cancer diagnosed 2 days after first dose of study drug).

For patients receiving combination therapy, causality will be assessed individually for each protocol-mandated therapy.

5.3.5 Procedures for Recording Adverse Events

Investigators should use correct medical terminology/concepts when recording adverse events on the Adverse Event eCRF. Avoid colloquialisms and abbreviations.

Only one adverse event term should be recorded in the event field on the Adverse Event eCRF.

5.3.5.1 Diagnosis versus Signs and Symptoms

A diagnosis (if known) should be recorded on the Adverse Event eCRF rather than individual signs and symptoms (e.g., record only liver failure or hepatitis rather than jaundice, asterixis, and elevated transaminases). However, if a constellation of signs and/or symptoms cannot be medically characterized as a single diagnosis or syndrome at the time of reporting, each individual event should be recorded on the Adverse Event eCRF. If a diagnosis is subsequently established, all previously reported adverse events based on signs and symptoms should be nullified and replaced by one adverse event report based on the single diagnosis, with a starting date that corresponds to the starting date of the first symptom of the eventual diagnosis.

5.3.5.2 Adverse Events That Are Secondary to Other Events

In general, adverse events that are secondary to other events (e.g., cascade events or clinical sequelae) should be identified by their primary cause, with the exception of severe or serious secondary events. A medically significant secondary adverse event that is separated in time from the initiating event should be recorded as an independent event on the Adverse Event eCRF. For example:

- If vomiting results in mild dehydration with no additional treatment in a healthy adult, only vomiting should be reported on the eCRF.
- If vomiting results in severe dehydration, both events should be reported separately on the eCRF.
- If a severe GI hemorrhage leads to renal failure, both events should be reported separately on the eCRF.
- If dizziness leads to a fall and consequent fracture, all three events should be reported separately on the eCRF.
- If neutropenia is accompanied by an infection, both events should be reported separately on the eCRF.

All adverse events should be recorded separately on the Adverse Event eCRF if it is unclear as to whether the events are associated.

5.3.5.3 Persistent or Recurrent Adverse Events Persistent Adverse Events First Reported in Study GS40868

A persistent adverse event is one that extends continuously, without resolution, between patient evaluation timepoints. Such events should only be recorded once on the Adverse Event eCRF. The initial severity (intensity or grade) of the event will be recorded at the time the event is first reported. If a persistent adverse event becomes more severe, the most extreme severity should also be recorded on the Adverse Event eCRF. If the event becomes serious, it should be reported to the Sponsor immediately (i.e., no more than 24 hours after learning that the event became serious; see Section 5.4.2 for reporting instructions). The Adverse Event eCRF should be updated by changing the event from "non-serious" to "serious," providing the date that the event became serious, and completing all data fields related to serious adverse events.

Persistent Adverse Events First Reported in the Parent Study

An adverse event that is ongoing at the end of the parent study will be marked as not resolved in the eCRF for that study and will be reopened in this study with the same start date, adverse event term, and severity recorded in the parent study. The severity should be evaluated by the investigator at the start of this study and updated in the Adverse Event Intensity or Grade Changes eCRF if applicable.

Recurrent Adverse Events

A recurrent adverse event is one that resolves between patient evaluation timepoints and subsequently recurs. Each recurrence of an adverse event should be recorded as a separate event on the Adverse Event eCRF.

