4.5.2 Medical History, Concomitant Medication, and Demographic Data

Medical history, including clinically significant diseases, surgeries, cancer history (including prior cancer therapies and procedures), and reproductive status, will be recorded at baseline in the parent study. In addition, all medications (e.g., prescription drugs, over-the-counter drugs, vaccines, herbal or homeopathic remedies, nutritional supplements) used by the patient from the time the patient completed the treatment period of the parent study will be recorded. Past resolved adverse events will be recorded in the medical history if clinically significant. Refer to Section 5.3.5.3 for information on recording adverse events that had not resolved at the end of the parent study. At the time of each follow-up physical examination, an interval medical history should be obtained and any changes in medications and allergies should be recorded.

Demographic data will include age, sex, and self-reported race/ethnicity.

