4.5.3 Physical Examinations

Limited, symptom-directed physical examinations should be performed at specified visits and as clinically indicated. Changes in parent study baseline abnormalities should be recorded in patient notes. New or worsened clinically significant abnormalities should be recorded as adverse events on the Adverse Event eCRF.

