Appendix 1: Schedule of Activities (Cont.)

BID=twice a day; CRP=C-reactive protein; CSU=chronic spontaneous urticaria; eCRF=electronic case report form; LDH=lactate dehydrogenase; OLE=open-label extension; PK=pharmacokinetics; PRO=patient-reported outcome; PhyGA-LS=Physician's Global Assessment of Disease Control-Likert Scale; Q4W=every 4 weeks; SC=study completion; SFU=safety follow-up; TD=treatment discontinuation; UAS=Urticaria Activity Score;UAS7=Urticaria Activity Score over 7 days; UCT=Urticaria Control Test; UV=unscheduled visit.

Note: (x)=optional/as clinically indicated.

- ^a Fenebrutinib tablets will be dispensed on site every 4 weeks. For periods in which study site visits (for assessments) are scheduled > 4 weeks apart, patients will be expected to visit site to receive allotment of study drug.
- ^b All assessments on Day 1 are conducted prior to study drug administration unless otherwise specified. Activities that were performed at final visit of the parent study, if within 3 months prior to Day 1, should not be repeated.
- ^c Patients who refuse to complete the safety follow-up period should return to the clinic for a treatment discontinuation visit.
- ^d Patients who discontinue study treatment will be asked to return to the clinic for a safety follow-up visit approximately 4 weeks after the last dose of study drug (see Section 4.6.1).
- ^e Concomitant therapy consists of any medication (e.g., prescription drugs, over-the-counter drugs, vaccines, herbal or homeopathic remedies, nutritional supplements) used by a patient in addition to protocol-mandated treatment from entry into the extension study to the final visit of the extension study. All such medications, including standard-of-care H₁-antihistamines for CSU, should be reported to the investigator and recorded on the Concomitant Medications eCRF.
- ^f After informed consent has been obtained but prior to initiation of study drug, only serious adverse events caused by a protocol-mandated intervention should be reported. After initiation of study drug, all adverse events will be reported until 4 weeks after the final dose of study drug. After this period, the Sponsor should be notified if the investigator becomes aware of any serious adverse event that is believed to be related to prior study drug treatment (see Section 5.6).
- ^g Includes measurement of pulse rate and systolic and diastolic blood pressure while the patient is in a seated position for at least 5 minutes

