- ^h Limited, symptom-directed physical examination should be performed on Day 1 and as clinically indicated. Changes in parent study baseline abnormalities should be recorded in patient notes. Record new or worsened clinically significant abnormalities on the Adverse Event eCRF.
- ⁱ ECGs can be performed without specific restrictions (e.g., can be performed at any time of day, before or after dosing, fasting or fed) but are to be obtained prior to other procedures scheduled at that same time (e.g., vital sign measurements, blood draws). ECG recordings must be performed after the patient has been resting in a supine position for at least 10 minutes. Circumstances that may induce changes in heart rate, including environmental distractions (e.g., television, radio, conversation) should be avoided during the pre-ECG resting period and during ECG recording.
- ^j Includes hemoglobin, hematocrit, platelet count, RBC count, WBC count, and percent and absolute differential counts (neutrophils, bands, lymphocytes, monocytes, eosinophils, basophils, other cells).
- ^k Includes bicarbonate or total carbon dioxide (if considered standard of care for the region), sodium, potassium, chloride, glucose, BUN or urea, creatinine, calcium, phosphorus, magnesium, total and direct bilirubin, total protein, albumin, ALT, AST, LDH, ALP, creatine phosphokinase, CRP, lipase, and uric acid.
- ^l Includes INR, aPTT, PT, and fibrinogen.

Fenebrutinib—Genentech, Inc.

68/Protocol GS40868, Version 1

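### Does the safety analysis need a written rule for adverse events that began before the first open-label dose?

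*Combined protocol and SAP*

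**What the plan says.** **Carried-over events.** Section 4.5.2 directs the reader: "Refer to Section 5.3.5.3 for information on recording adverse events that had not resolved at the end of the parent study". Section 5.3.5.3 then says that such an event "will be reopened in this study with the same start date, adverse event term, and severity recorded in the parent study". The investigator re-rates its severity when this study starts and enters any change on a separate intensity-change form.

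**Examination findings.** Section 4.5.3 says: "New or worsened clinically significant abnormalities should be recorded as adverse events on the Adverse Event eCRF". Appendix 1 note h says: "Limited, symptom-directed physical examination should be performed on Day 1 and as clinically indicated", and adds: "Record new or worsened clinically significant abnormalities on the Adverse Event eCRF". Note b says: "All assessments on Day 1 are conducted prior to study drug administration unless otherwise specified".

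**Reporting window.** Under note f, once consent is given but "prior to initiation of study drug, only serious adverse events caused by a protocol-mandated intervention should be reported". Section 5.3.1 has the same pre-dose limit and continues: "After initiation of study drug, all adverse events will be reported until 4 weeks after the final dose of study drug".

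**Preexisting conditions.** Section 5.3.5.8 treats a condition found at the Day 1 visit as preexisting. It goes on the medical history form and becomes an adverse event only if it worsens during the study.

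**Analysis.** Section 2.1 lists the incidence and timing of adverse events as the first endpoint of the primary safety objective. Section 6.4 defines the safety population as patients with at least one dose and provides for MedDRA coding, severity grading and descriptive summaries. It gives no rule on onset date and does not mention reopened events.

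**The concern.** There are two apparent problems.

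The first is about recording. The Day 1 examination precedes dosing, yet Section 4.5.3 and note h send new or worsened abnormalities to the adverse event form. Both mention the parent-study baseline. A non-serious finding that arose after that baseline and is seen on Day 1 might therefore be recorded as an adverse event at one site and as medical history at another.

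The second is about analysis. Reopened events carry start dates that precede the first open-label dose. If every entry is tabulated, an event that began on parent-study placebo could count toward open-label fenebrutinib and have an onset time before dosing. If entries are filtered on start date alone, a carried-over event that worsens on open-label drug drops out. Section 3.1 notes that some patients first receive fenebrutinib in this study, so what counts as an event on open-label drug is a fair question to ask of a primary safety endpoint.

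**Working it through.** The plan states no figure on this point, so the check is mainly a comparison of sections.

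**1. Do the recording rules contradict each other?**

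- In both Section 4.5.3 and note h, the parent-study baseline appears in the sentence about what goes into patient notes. The sentence about the adverse event form names no reference point.
- The opening of Section 5.3 makes the recording and reporting of adverse events follow Section 5.3 itself, together with Sections 5.4 to 5.6. Sections 5.3.1 and 5.3.5.8 are therefore the operative rules.
- Section 5.3.5.8 supplies the missing reference point. A condition present on Day 1 is preexisting in this study, so it is not new and becomes an adverse event only on worsening.
- Section 4.5.3 covers examinations at all visits, while Section 5.3.1 addresses the pre-dose period specifically. In the Appendix 1 schedule, the adverse event row carries note f.

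Read this way, the sections agree. A pre-dose, non-serious Day 1 finding goes to medical history.

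**2. How many patients could fall where the wording is loose?**

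- Section 4.5 and note b say that a Day 1 assessment is not repeated if it was done at the final parent-study visit within the preceding 3 months.
- Section 4.1.2 excludes patients with clinically significant infection since the parent treatment period, and those with later changes judged to raise adverse event risk.
- Unresolved parent-study events follow Section 5.3.5.3.

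What remains is a non-serious but clinically significant finding that was never a parent-study adverse event, in an eligible patient who is examined on Day 1. The documents do not allow a count.

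**3. Can the main summary be built from what is collected?**

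| Entry | Information available | Natural handling |
|---|---|---|
| Onset after first open-label dose | Start date, severity | Counted |
| Carried over, unchanged | Original start date, term, severity | Listed separately |
| Carried over, then worse on open-label drug | As above, plus severity change | Counted as worsening |
| Present on Day 1, not a parent-study event | Medical history form | Not counted unless it worsens |

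The counting window follows from Section 5.3.1 (initiation of study drug to 4 weeks after the final dose), and the safety population already requires a dose. No further data are needed.

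**4. Weight of one patient.** With N = 165, the maximum in Section 3.1:

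- one patient: 1/165 = 0.00606, or 0.61 percentage points;
- five patients, for scale only: 5/165 = 0.0303, or 3.0 percentage points.

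Because 165 is a maximum, each patient weighs more if fewer enroll. These figures are the weight of any patient in a study of this size. They do not estimate how often carry-over occurs, and the documents give neither a carry-over rate nor an adverse event rate.

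**The case for a change.** The strongest case for a change is that neither simple default is right. Counting every entry brings in unchanged events, and filtering on start date loses those that worsen. The severity re-rating at study start may itself precede dosing. Section 6.5 promises a data analysis plan, but only for efficacy, and Section 6.4 does not refer to one. Section 6.8 allows data cuts to be submitted with the parent study, where an event left open in one database and reopened in the other could appear twice. Section 5.7 has the sponsor compare cumulative event frequency with the Investigator's Brochure.

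Part of this stands. Section 6.4 is silent, and a sentence on tabulation in the analysis plan would be good practice. The rest carries less weight. An onset-or-worsening rule is the ordinary choice in an extension study and avoids both faulty defaults. A reopened event keeps its term and start date, so duplicates can be matched when the two studies are combined. The comparison in Section 5.7 belongs to expedited safety reporting and does not depend on how the final tables are laid out. The time origin for onset could be the first open-label dose or the first fenebrutinib dose ever. Either is defensible, so leaving it open is not an error.

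**Conclusion.** No change to the plan follows. The apparent contradiction over the Day 1 examination comes from attaching the parent-study baseline to a sentence that does not mention it. Sections 4.5.3, 5.3.1 and 5.3.5.8 can be applied together, and the missing cross-reference from 5.3.5.8 to 5.3.5.3 is editorial, since Section 4.5.2 already points there. The remaining gap, how reopened events are tabulated, is detail that analysts can settle before any table is produced.

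The effect on results is not shown and may be zero. No hypothesis test, sample size or estimate of efficacy depends on it. The conclusion rests on two assumptions: that start dates are kept as Section 5.3.5.3 requires, and that the intensity-change form lets worsening be placed before or after the first open-label dose. The documents name that form but do not show its fields.
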